
mini-vaccination stations in communities highly impacted by the pandemic and identifying individual and structural barriers to COVID-19 immunization (Phase 2). Specific aims include:

Aim 1. To evaluate the preliminary impact of 2VIDA! compared to the standard-of-care for COVID-19 vaccination services among Latinx and AA adults ≥ 16 years (N=1000) in San Diego. We will use a 2-armed randomized controlled trial (RCT)* where Latinx and AA adults ≥ 16 years or older from six participating community health centers (CHC) and surrounding communities will be assigned to the 2VIDA! intervention (n=3 CHC; N=500 participants) or to the control site (e.g., standard of care) (n=3 CHC; N=500 participants). Data will be collected on a) sociodemographic characteristics; b) characteristics associated with social marginalization; c) access to and utilization of health care; d) vaccination history, interest, hesitancy and uptake; e) perceptions of the COVID-19 vaccine (e.g., fears, myths, etc.); f) general health; and h) trust in government, research, and social agencies, i) satisfaction with 2VIDA!; at baseline and 4-week follow-up. We hypothesize that at follow-up, compared to control participants, 2VIDA! participants will:

H.1. have increased knowledge about the COVID-19 vaccine (including medically accurate information, benefits, and risks);
H.2. more likely to receive the COVID-19 vaccine;
H.3. more likely to complete vaccine series (based on Centers for Disease Control and Prevention [CDC] recommendations).¹

Aim 2. To assess feasibility, acceptability, and intervention effects of 2VIDA! To assess feasibility and acceptability, we will utilize quantitative methods to track recruitment, condition assignment, participant retention, intervention implementation, and potential threats (e.g., contamination). We will also utilize qualitative methods to assess acceptability via focus groups with participants to understand potential for broad implementation (e.g., what components did they receive of the intervention, client satisfaction, linkage to COVID-19 services). To assess intervention effects, we will examine participant vaccination rates/completion across both groups.

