Spanish that are written at the 8th grade level (the average reading level of adults in the United States) that peer-health educators will distribute to community members during their visits to the participating SYH community centers, door-to-door, local supermarkets (SYH has a partnership with Northgate Gonzales Market), and community-based organizations (CBO's) in the selected communities. These materials have general information on COVID-19 as well as educational information and resources regarding COVID-19 prevention, symptoms, testing, contact tracing, COVID-19 vaccine (how it works, technology used, administration [2-dose series and importance of vaccine completion], safety concerns, benefits, risks, dispelling common misconceptions and misinformation, potential side effects and what to do), and other topics identified based on community needs. This information will be updated monthly to ensure the most up to date information. The goal is to distribute approximately 20,000 educational and outreach materials across the three randomly selected communities.

- **COVID-19 Community Outreach & Health Promotion.** Peer-health educators will work with local CBO's and facilitate a combination of live broadcast sessions, pre-recorded webinars, social media posts, and other outreach activities in English and Spanish reaching community members with information on the above COVID-19 related topics as well as other identified needs such as what to do if a family member is infected and where you can get the COVID-19 vaccine. The goal of this research activity is to reach 10,000 viewers (per session) in the various social media platforms in the three randomly selected communities.
- **COVID-19 Individual Health Education & Linkages to Medical and Supportive Services.** For the purposes of this research, SYH will establish a COVID-19 Resource Center within the participating health centers in the three randomly selected communities (intervention sites only) providing individual COVID-19 related health education and linkages to medical and supportive services for patients and community members in need of additional education and support regarding COVID-19 disease and COVID-19 vaccine.

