Cover Page for ClinicalTrials.gov

Document: Statistical Analysis Plan

Official Study Title: Project 2VIDA! COVID-19 Vaccine Intervention Delivery for Adults in Southern California

NCT number: NCT05022472

Document date: February 5, 2021

STATISTICAL DESIGN AND POWER CALCULATIONS

We will approach overall data analyses using a multivariate repeated measures design (i.e., doubly multivariate) to assess mean differences in treatment and control groups on our primary (acceptance of COVID-19 vaccine and vaccine series completion) and secondary outcome variables (increased knowledge of COVID-19 vaccine, increased access to COVID-19 vaccine, vaccine hesitancy). Additional measures at baseline and follow-up will be used as covariates (e.g., outreach and health communication, vaccine hesitancy or mistrust). Mean differences, both within and between treatment and control groups as well as group by treatment interaction effects will be analyzed. The targeted sample size is sufficient to detect a small effect size (.20) with power = .90 at alpha = .05 accounting for moderate participant attrition. Descriptive Statistics. To describe the overall sample regarding demographics, structural and individual barriers, and potential covariates of intervention effects at baseline, prevalence statistics and means and standard deviation will be provided for all baseline variables; Cronbach's alpha of .70 will be required to be considered reliable. Baseline Analyses to Detect Differences Between Treatment Groups. Chi-square analyses and paired t-tests will be used to detect differences in demographics, knowledge of COVID-19 vaccine, access to COVID-19 vaccine, acceptance of COVID-19 vaccine and series completion, COVID-19 resource-seeking behaviors and linkage into care between intervention and control groups. Demographic variables included in these analyses will be age, gender, race/ethnicity, household income, marital status, and having insurance. Those variables differing across treatment groups at the $p < .20$ level will be included in subsequent adjusted outcome analyses.

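### Adjusting for outreach and health communication, and possibly for resource-seeking and linkage into care, may condition on part of 2VIDA! and bias the arm effect, most likely toward zero

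*SAP*

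**What the plan says.** The SAP's single section and the Data Analysis paragraph of Protocol Section 8 carry essentially the same text. Two sentences put variables into the outcome models.

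- The first has no entry condition and covers both time points: "Additional measures at baseline and follow-up will be used as covariates (e.g., outreach and health communication, vaccine hesitancy or mistrust".
- The second is a screen. Under Baseline Analyses, the arms are compared on demographics, knowledge, access, acceptance and completion, and on "COVID-19 resource-seeking behaviors and linkage into care between intervention and control groups". A sentence listing the demographic variables follows. The next sentence says that variables differing at p < .20 "will be included in subsequent adjusted outcome analyses".

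Protocol Section 8, Phase I, describes the intervention. Its components are individual awareness and education, community outreach and health promotion, and "COVID-19 Individual Health Education & Linkages to Medical and Supportive Services". For the last of these, "SYH will establish a COVID-19 Resource Center within the participating health centers in the three randomly selected communities (intervention sites only"). The note closing Section 5 says that no 2VIDA! component is deployed at control sites.

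Neither document defines the three measures, limits covariates to variables fixed before Phase I, designates an unadjusted primary analysis, or plans a mediation analysis.

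**The concern.** A covariate belongs in the primary model of a randomized comparison if the assigned condition cannot move it. Outreach and health communication, resource-seeking, and linkage into care look like things that 2VIDA! is designed to move. If so, the adjusted arm coefficient estimates the effect of 2VIDA! apart from whatever acts through those channels, which is not the question in Aim 1. The coefficient is also less precise, because the covariate tracks arm. The p < .20 rule adds to this, since it is most likely to admit such a variable when Phase I was delivered well.

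The usual remedy is to use baseline values only. Here it may not work, because the baseline survey is taken in Phase II, just before vaccination is offered, when Phase I appears to be already under way. A program that works could then be reported as having little effect, and no other planned analysis would show why.

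**Working it through.** **1. Match of constructs**

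| Covariate or screened variable (SAP) | 2VIDA! component (Protocol Section 8, Phase I) | Route into the model |
|---|---|---|
| Outreach and health communication | Community outreach and health promotion | Named directly, baseline and follow-up |
| Linkage into care | Individual education and linkages to services | p < .20 screen, on one reading |
| Resource-seeking behaviors | Resource Center, intervention sites only | p < .20 screen, on one reading |

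**2. Timing.** Clinics, not individuals, are randomized (Section 10). Participants complete the baseline survey and are then offered the vaccine (Section 8, Phase II). The stations reuse the Phase I logo and illustrations so that people recognize them. Satisfaction with 2VIDA! appears in the list of items collected at baseline and at 4 weeks. Together these suggest exposure before the baseline survey, but no sentence says so.

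**3. The plan's power figure.** The plan states power .90 for an effect of .20 at alpha .05, with 500 per arm and moderate attrition. A two-sided test without attrition gives Φ(.20 × √(500/2) − 1.96) = Φ(3.162 − 1.96) = .885; .90 needs 526 per arm. A one-sided test needs 429 per arm, which tolerates 1 − 429/500 = 14% attrition. Sidedness, attrition rate and baseline correlation are not stated, so .90 can be neither confirmed nor called wrong. I use .885 as the reference.

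**4. Cost of adjustment (assumed exposure rates).** Let a1 and a0 be the proportions exposed in the intervention and control arms, and p their mean.

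- Correlation with arm: r = .5(a1 − a0)/√(p(1 − p))
- Standard error multiplier: 1/√(1 − r²)
- Adjusted effect: total effect minus the part running through the covariate
- Power: Φ(effect × √250 / multiplier − 1.96)

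For 70% v 20%: p = .45, r = .25/.4975 = .503, variance inflation 1/(1 − .2525) = 1.338, multiplier 1.157. If half of .20 SD runs through the covariate, the adjusted effect is .10 and power is Φ(1.581/1.157 − 1.96) = Φ(−.593) = .28. Residual SD is held at 1.

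| Exposure | r | SE multiplier | Power, half through covariate (effect .10) | Power, none through covariate (effect .20) |
|---|---|---|---|---|
| 50% v 20% | .314 | 1.05 | .32 | .85 |
| 70% v 20% | .503 | 1.16 | .28 | .78 |
| 90% v 10% | .800 | 1.67 | .16 | .475 |

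The last column isolates the loss from the standard error alone, against .885 unadjusted.

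**5. Risk-difference scale, since vaccination and completion are yes/no.** With a total difference of .10, an arm difference a in the covariate and a covariate effect b, the adjusted difference is .10 − a·b:

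- a = .05, b = .1: .095
- a = .10, b = .2: .08
- a = .20, b = .3: .04
- a = .30, b = .3: .01

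**6. Entry under p < .20 (500 per arm, clinics ignored).** Intervention v control proportions of 13% v 10% enter with probability .58, 15% v 10% with .87, and 30% v 20% with .99.

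**7. Direction.** Simulation with 500 per arm and 400 runs; exposure is about 10% v 40% (control v intervention) when the covariate differs by arm and no common cause is added:

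| Scenario | Unadjusted | Adjusted |
|---|---|---|
| Covariate does not differ by arm | .196 | .196 |
| Covariate has no effect on outcome | .196 | .194 |
| Half of effect through covariate | .193 | .092 |
| All of effect through covariate | .201 | −.001 |
| Half through it; common cause raises covariate and outcome | .208 | −.041 |
| Half through it; common cause lowers covariate, raises outcome | .195 | .242 |
| Covariate itself lowers outcome | .143 | .201 |

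**The case against.** The strongest reply is that the measures are undefined. The survey domains in the protocol contain no item on linkage, resource-seeking or outreach. The nearest is access to and use of health care, which need not refer to 2VIDA!, and control participants recruited around health centers can also seek resources or be linked to care. This stands as a limit: that the variables record receipt of 2VIDA! is a strong inference from the component names, not a stated fact. It does not remove the point, because nothing in the plan prevents that use.

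The p < .20 sentence directly follows the demographic list and may mean demographics only. On that reading resource-seeking and linkage never reach the outcome model. Outreach and health communication still does, because it is named without a screen.

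A reader might infer four stronger things, which the documents do not support.

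- That adjustment holds the whole treatment constant. It does not: mini-vaccination stations, second-dose reminders and tracing through contacts are on neither list, and they bear directly on uptake and completion.
- That the arm effect must shrink. Step 7 shows no change in two cases and enlargement in two.
- That Aim 2 counts linkage as a component received. It lists "what components did they receive of the intervention, client satisfaction, linkage to COVID-19 services" as separate focus-group topics.
- That the variables would be lost for monitoring delivery. A covariate can still be reported, and Aim 2 already plans quantitative tracking of implementation and contamination.

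**Conclusion.** The concern holds in a limited form. As written, the plan adjusts for outreach and health communication and, on one reading, for resource-seeking and linkage into care. These closely resemble Phase I components that controls are not meant to receive. Doing so may condition on part of the intervention and bias the arm effect, most likely toward zero, with a larger standard error. Restricting to baseline values may not help, because Phase I appears to come first.

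The size cannot be read from the documents. In the hypothetical cases with half the effect mediated, power falls from .885 to between .16 and .32. On the risk-difference scale, between 5% and 90% of a .10 effect is lost across the values shown. These figures rest on assumed exposure and mediation rates, a single binary covariate, no common cause and no clustering. The power figures also assume a continuous outcome. Since six clinics are randomized, .885 is a reference value and not the trial's power. The change should be made because it is cheap and neither document guards against the problem.

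**What to change.** Make the same edits in the SAP and in the Data Analysis paragraph of Protocol Section 8.

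1. Remove outreach and health communication, resource-seeking behaviors and linkage into care from the covariates and from the p < .20 screen.
2. Limit adjustment in the primary model to prespecified characteristics that 2VIDA! cannot change, such as age, gender, race/ethnicity, education and income. Education is in the protocol's demographic list but not the SAP's, so align the two.
3. Report the three removed variables by arm and clinic, as process measures in the intervention arm and contamination measures in the control arm. Define each item so that the reports can be interpreted.
4. Label any analysis that adjusts for them as exploratory mediation.

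The cost is a wording change in two documents, with the protocol amendment that this entails. The three variables can still be collected and reported.

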Acceptance and uptake of COVID-19 vaccines will be instrumental to ending the pandemic, however, public confidence in vaccination is fragile, especially among racial and ethnic minorities. A recent nationally representative longitudinal study found that the public's likelihood of getting a COVID-19 vaccine declined from 74% in early April to 56% in early December 2020, despite the press releases in November 2020 of a high vaccine efficacy for 2 vaccines in phase 3 trials and the surge in cases during this timeframe.¹⁴ Likewise, self-reported likelihood of getting COVID-19 vaccination was lower among women, AA individuals, and those with lower educational backgrounds. Similarly, other studies have indicated that Latinx are less likely to trust the vaccine and that there is skepticism among Latinx communities across the country¹⁵ due to unequal access to health care, the lack of reliable information (especially in Spanish), coupled with disinformation.¹⁶ These findings highlight the mistrust between racial and ethnic minorities and public health officials, likely due to historical racism in health care and implicit bias.⁵ This is concerning due to their disproportionately higher burden from COVID-19 disease and because high levels of vaccination are necessary to reach herd immunity and control the pandemic. These findings emphasize the need for interventions that address these barriers and rebuilt trust in our communities of color. The proposed study is significant in that it will conduct extensive individual and community level awareness, education, outreach and health promotion that center on providing COVID-19 medically accurate and culturally competent information (in English and Spanish at 8th grade level) in order to empower our communities of color.

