PHASE II. To evaluate the preliminary impact of 2VIDA! compared to the standard-of-care for COVID-19 vaccination services among Latinx and AA adults >16 years (N=1000) in San Diego. During Phase 2 we will offer the COVID-19 vaccine at the participating SYH community health centers and mini-vaccination stations that will be set-up in these communities (only intervention sites) as part of the intervention efforts (i.e., research activities) to increase access and uptake of the COVID-19 vaccine. We have identified various open spaces (e.g., public parks) in these communities to set-up the vaccination stations. SYH is currently offering the vaccine in their facilities as part of their standard of care. It is available to everyone who is eligible according to the state guidelines and does not depend on participating in this study. However, as part of 2VIDA! we will add these mini-vaccination stations to increase access to the vaccine (e.g., open after 5:00pm and on the weekends). Furthermore, data will be collected to assess individual, social, and contextual factors related to access, acceptance, and uptake of the COVID-19 vaccine including: a) sociodemographic characteristics; b) characteristics associated with social marginalization (e.g., homelessness, food insecurity); c) access to and utilization of health care; d) vaccination history, interest, hesitancy and uptake; e) perceptions of the COVID-19 vaccine (e.g., fears, myths, etc.); f) general health; and h) trust in government, research, and social agencies; i) satisfaction with 2VIDA! at baseline and 4-week follow-up. The survey will last approximately 20 minutes and will be self-administered in both English and Spanish. Following the survey participants will be offered the COVID-19 vaccine and the SYH staff will help them set-up an online appointment onsite for the 2nd dose (1 month follow-up) and will be asked to complete a 5 min survey during the follow-up visit. SYH has trained medical staff and a strict protocol for the storage, handling, and application of the vaccine. UCSD staff will not be involved in this process. Furthermore, participants will be asked to provide separate written consent in order to receive the vaccine that will be conducted by SYH staff. Additionally, two focus groups (FGs) will be conducted with members of Latinx and AA communities (n=8-10 participants per group) to obtain feedback on implementation and ways to improve future sustainability and scalability for future vaccination efforts among vulnerable underserved communities. FGs will be transcribed and reviewed for themes specific to 2VIDA! including personal and structural barriers to medical accurate information and the COVID-19 vaccine, benefits, challenges, feasibility, and scalability.

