Focus Groups (FG). Two separate FGs (one in English and one in Spanish) will be conducted (n=2; 8-10 participants per group) following the implementation of *2VIDA!* with members of the Latinx and AA community in San Diego to understand the socio-structural barriers to COVID-19 information and resources (e.g., testing) and vaccine uptake (e.g., medical mistrust, discrimination, stigma, transportation, access to vaccination site, lack of insurance) as well as acceptability of the *2VIDA!* intervention. Participants will be recruited from six SYH community health centers (from both intervention and control sites) that are located in the communities with the highest cases of COVID-19. Eligibility criteria includes: 1) identify as Latinx or African American, 2) 16 years of age or older, 3) reside in one of the target communities (National City, Lincoln Park, Logan Heights, Valencia Park, San Ysidro), 4) literate in English or Spanish, 5) able to provide written and informed consent (including permission to record FG session). We will recruit equal number of Latinx and AA participants for each session, as well as equal number of individuals who both have and haven't received the vaccine as part of *2VIDA!* to provide an in-depth discussion and have a better understanding of the community needs. The FGs will take place based on the time/date that is most convenient for the community members. Each FG will take place in the private conference room located in the clinics, will follow a semi-structured open-ended guide, last between 60-90 minutes and be facilitated by a moderator ([name]) and note-taker (who also records each session). This data will allow us to identify structural barriers, acceptability, and feasibility of *2VIDA!* on COVID-19 vaccination uptake.

Data Analysis. We will approach overall data analyses using a multivariate repeated measures design (i.e., doubly multivariate) to assess mean differences in treatment and control groups on our primary (acceptance of COVID-19 vaccine and vaccine series completion) and secondary outcome variables (increased knowledge of COVID-19 vaccine, increased

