access to COVID-19 vaccine, vaccine hesitancy). Additional measures at baseline and follow-up will be used as covariates (e.g., outreach and health communication, vaccine hesitancy or mistrust). Mean differences, both within and between treatment and control groups as well as group by treatment interaction effects will be analyzed. The targeted sample size is sufficient to detect a small effect size (.20) with power = .90 at alpha = .05 accounting for moderate participant attrition.

Descriptive Statistics. To describe the overall sample regarding demographics, structural and individual barriers, and potential covariates of intervention effects at baseline, prevalence statistics and means and standard deviation will be provided for all baseline variables; Cronbach's alpha of .70 will be required to be considered reliable. **Baseline Analyses to Detect Differences Between Treatment Groups.** Chi-square analyses and paired t-tests will be used to detect differences in demographics, knowledge of COVID-19 vaccine, access to COVID-19 vaccine, acceptance of COVID-19 vaccine and series completion, COVID-19 resource-seeking behaviors and linkage into care between intervention and control groups. Demographic variables included in these analyses will be age, gender, race/ethnicity, education, household income, marital status, and having insurance. Those variables differing across treatment groups at the $p < .20$ level will be included in subsequent adjusted outcome analyses. For the qualitative data analysis, final translated electronic transcripts will be imported into Dedoose. Analysis will be done through identification of recurrent themes following Crabtree and Miller's 5 step "interpretive process."¹⁹ First, transcripts will be read to identify common themes, codes will be developed and ~10% of data will be double coded and inter-rate reliability assessed. Coded text will be extracted and organized and read to identify emergent themes.⁶⁵ Matrices will be created to compare codes by themes (e.g., medical mistrust, discrimination, stigma, transportation, access to vaccination site, lack of insurance). Data will be utilized to refine *2VIDA!*, assess acceptability, and inform future vaccination efforts among underserved communities.

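### Survey language (English or Spanish) is not among the demographic variables compared between arms and screened for adjustment, and three clinics per arm cannot be relied on to balance it

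*SAP*

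**What the plan says.** The SAP compares the arms at baseline on a named set of demographic variables: "Demographic variables included in these analyses will be age, gender, race/ethnicity, household income, marital status, and having insurance". The protocol's Data Analysis text (section 8) has the same sentence with education added: "Demographic variables included in these analyses will be age, gender, race/ethnicity, education, household income, marital status, and having insurance". Language is in neither list.

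Two further provisions matter. First, the comparison also covers non-demographic measures: the SAP tests for "differences in demographics, knowledge of COVID-19 vaccine, access to COVID-19 vaccine, acceptance of COVID-19 vaccine and series completion", and then for resource seeking and linkage to care. "Those variables differing across treatment groups at the" p < .20 level go into the adjusted models. Second, a separate clause allows more covariates by example: "Additional measures at baseline and follow-up will be used as covariates (e.g., outreach and health communication, vaccine hesitancy or mistrust".

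Language appears elsewhere in the protocol. Section 6 (Background and Significance), discussing skepticism in Latinx communities, cites "the lack of reliable information (especially in Spanish") alongside unequal access to care and disinformation. Under Phase II of section 8 the survey "will be self-administered in both English and Spanish". The focus groups are divided by language: "Two separate FGs (one in English and one in Spanish) will be conducted". Literacy in either language is an inclusion criterion.

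Section 10 (Recruitment) randomizes six clinics evenly. No stratification, matching or constraint is described.

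**The concern.** If Spanish and English respondents differ in how readily they take up or complete vaccination, and one arm has more Spanish respondents, part of the observed arm difference reflects language mix rather than the intervention. It could add to a true effect or mask one. The listed comparisons need not show the imbalance, and no rule commits the analysis to adjusting for it.

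Race/ethnicity is an incomplete substitute. It separates Latinx from African American participants, but Latinx participants may answer in either language.

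Two features of the design make the risk larger than in an individually randomized trial of 1,000. Only three clinics per arm average out whatever differences exist between clinics. In addition, participants join after their clinic has been assigned. Only the intervention communities receive the bilingual outreach and the park vaccination stations, and the stations are also recruitment points. The language mix could therefore differ through who is reached, as well as by chance.

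**Working it through.** **The plan's own figure.** The documents give no figure on language. Their one quantitative claim is power .90 for an effect of .20 at alpha .05. A two-sided comparison of two means with 500 per arm, no attrition and no clustering gives 0.885, close to that claim. It does not bear on this point. The .20 serves below only as a yardstick. Read as Cohen's h from an assumed 50% uptake, it gives sin²((2·arcsin√0.5 + 0.20)/2) = 0.599, a difference of about 9.9 points.

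**Inputs.** From the documents: six clinics, three per arm, 500 participants per arm. Assumed, because the documents are silent: each clinic's Spanish share, equal clinic sizes, and the uptake gap *g* between language groups (10 to 20 points).

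**Step 1: imbalance in language mix.** Let *D* = |mean Spanish share of the three intervention clinics − mean share of the three control clinics|. There are 6!/(3!·3!) = 20 allocations, in mirror-image pairs, so ten distinct splits.

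- Wide spread (80, 70, 60, 40, 30, 20%). The extremes are (80+70+60)/3 − (40+30+20)/3 = 70 − 30 = 40, and (80+40+30)/3 − (70+60+20)/3 = 50 − 50 = 0. All ten splits: 40, 26.7, 20, 20, 13.3, 13.3, 13.3, 6.7, 6.7, 0. The mean is 160/10 = 16.0 points; 40% of allocations reach 20 or more.
- Mild spread (65, 60, 55, 45, 40, 35%). Every deviation from 50% is half as large, so every *D* halves: mean 8.0, maximum 20.

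In each scenario 2 of the 20 allocations balance exactly. Differences under 7 points occur in 30% of allocations (wide) and 60% (mild).

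**Step 2: shift in the arm contrast.** With no true effect and no adjustment, shift = *g* × *D*.

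| Assumed clinic shares | Mean *D* | Max *D* | Mean shift, *g* = 10 to 20 points | Max shift |
|---|---|---|---|---|
| 35–65% | 8 | 20 | 0.8 to 1.6 | 2 to 4 |
| 20–80% | 16 | 40 | 1.6 to 3.2 | 4 to 8 |

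The yardstick is about 10 points.

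**Step 3: does the assumed 50% average drive this?** No. *D* depends on the spread between clinics, not on the overall level. Shares of 40, 35, 30, 20, 15 and 10% (average 25%) have the same deviations as the mild scenario and give the same *D*.

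**Step 4: sensitivity to spread.** Simulating six clinics of 167 with an average share of 50% and a between-clinic SD of 5 to 25 points gives a mean *D* of 4.1 to 16.7 points. Individual randomization of 500 per arm would give 2.5.

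**Step 5: would adding language to the p < .20 screen be enough?** At 500 per arm, ignoring clinic, the screen flags a difference above 1.2816 × √(0.5/500) = 4.1 points. Applied to the clinic shares above, it flags 18 of 20 wide allocations and 14 of 20 mild ones. Screening would catch most large imbalances, but it leaves the outcome model to be settled by the baseline data.

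**The case against.** The case against has real force.

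- **The covariate set is not closed.** A reader might infer that language cannot enter the analysis at all. Only the demographic list is fixed; the clause on additional measures is open and gives mistrust as an example, which is one route by which language might act. This stands. But the clause does not name language, it admits measures taken at follow-up, and hesitancy is itself a secondary outcome, so it is not a dependable substitute for a fixed baseline trait.
- **Baseline measurement absorbs part of the problem.** A reader might infer that any scoring difference between the two survey versions becomes an arm difference. If each participant uses the same version twice, a constant difference largely cancels in a comparison of change. This stands for knowledge and hesitancy. It helps less for receipt and completion, because the vaccine is offered after the baseline survey.
- **Race/ethnicity may be a close proxy.** Section 10 aims for equal Latinx and Black representation. If that is met and African American participants answer in English (assumption), a 50% Spanish share would mean that all Latinx participants use Spanish. Race/ethnicity would then capture language almost fully, provided it passes the p < .20 screen. If Latinx participants split between versions, the proxy weakens and the average share falls, but step 3 shows that a lower average alone does not reduce the imbalance.
- **The protocol does not establish language as a driver of trust.** Section 6 speaks of information supply, as one cause among several. Bilingual materials and separate focus groups are delivery arrangements. This stands: language is a plausible covariate, not a demonstrated one.
- **Chance imbalance belongs in the standard error.** A standard error that accounts for clinic would reflect it. This is correct for chance imbalance, but it would not cover a systematic difference from recruitment after assignment, and the SAP describes no clinic term.

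**Conclusion.** The omission is real, and its consequence is modest. Language is in neither demographic list and is named nowhere else as a covariate. Three clinics per arm cannot be relied on to balance it, although some allocations would; the documents do not support saying that six clinics cannot balance it. An imbalance can enter the arm contrast, chiefly for vaccine receipt and completion. The documents also do not support saying that it passes in full into every outcome.

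Under the assumed shares and uptake gap, the average shift is 0.8 to 3.2 points, with a maximum of 2 to 8 in the least favorable allocations. Both assumptions are unsourced, and the figures allow nothing for absorption by race/ethnicity, mistrust or baseline measures. They show possible scale and do not estimate bias in this trial. The point is secondary to the missing clinic-level term, which affects every outcome whatever the language mix.

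**What to change.** Amend the SAP to:

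1. report baseline survey language (English or Spanish) by arm and by clinic;
2. include it as a fixed participant-level baseline covariate in the outcome models, whatever its baseline p-value;
3. fit those models with clinic accounted for.

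The cost of items 1 and 2 is SAP wording and one binary term. The value should be available from the survey version each participant completed; the documents do not say that this is stored as a field, so the sponsor should confirm it. No new data collection should be needed. Because language varies within clinics, the term is estimated largely from within-clinic differences and does not use up the few clinic-level degrees of freedom (six clinics minus two arms = 4). The same edit is the natural place to reconcile education, which the protocol lists and the SAP leaves out.
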